6.3.9. Visit 14: Concluding or end of study examination

This visit will take place 3 months after Visit 13, i.e., approximately 30 months after the first administration of study treatment (Visit 1), with a permitted deviation of up to 14 calendar days.

If a patient on trial relapses, or if the patient withdraws for any reason, including toxicity, they will also be asked to return to Moffitt for this end of study visit.

If the thirteenth study treatment administration had to be postponed (refer to Section 5.2.1.1 for criteria for postponement of study treatment), the concluding Visit should be scheduled 3 months after the actual date of the last administration.

[figure not shown]
The following procedures will be performed:

- A CT scan of the neck, chest and upper abdomen and pelvic CT scans.
- Physical examination (as at Visit 1).
- Recording of (serious) adverse events and pIMD.
- Blood sampling (15 ml as described in Section 6.4.2) for laboratory safety assays.
- Blood sampling (10 ml as described in Section 6.4.2) for humoral immunity assays.
- Blood sampling of 80 ml for cellular immune assays

In addition, these samples could be used for translational research for patients having given their specific informed consent to this.

- Pregnancy test for females of childbearing potential.
- Recording of concomitant medications.
- Treatment conclusion.

6.3.10 Post-treatment follow-up

- a. For procedures of Visit 14 - concluding visit, refer to Section 6.3.9 .
 b. For 5-year follow-up of patients who have completed the treatment phase, refer to Section 6.3.10.2.
 c. For 5-year follow-up of patients who have not completed the treatment phase, refer to Section 6.3.10 2.
 d. Five-year follow-up is performed until five years after first administration or until recurrence of disease.

6.3.10.1. Follow-up of patients who have completed the study treatment

CONFIDENTIAL

For patients who have completed the study treatment (up to and including Visit 14), follow-up visits will take place every 6 months after the concluding visit (Visit 14) for a maximum of 5 years after first study treatment administration.

The following procedures will be performed:

- A routine physical examination including assessment of ECOG performance status. Determination of disease status, on the basis of the patient's medical records and all other available information. If the patient has relapsed, the investigator will obtain information about the recurrence (date, type), as far as this is possible.
- CT scan of the neck, chest and upper abdomen as well as the pelvis (at Months 36, 48 and 60, or at any other time if clinically indicated).
- Recording of pIMD.
- Recording of SAEs related to study participation and concurrent medications.
- In addition, one year after the concluding visit, a blood sample (10 ml as described in Section 6.4) will be taken for humoral immunity testing.

Follow-up visits will be numbered consecutively from Visit F1 onwards. Findings at these visits will be recorded using Moffitt CRFs.

If relapse of disease is established at one of the follow-up visits, no further follow-up visits will take place. As for patients who have withdrawn from the study treatment (Section 6.3.10.2) because of disease relapse, annual post study contacts, e.g., by telephone, will be instituted and continued up to 5 years after the first study treatment administration.

6.3.10.2. Follow-up of patients who were withdrawn from the study treatment

Patients will be free to withdraw from the study at any time and for any reason and without prejudice to their further treatment. However, all patients who have withdrawn from study treatment will be examined at least 30 days after the last administration of study treatment and before starting any other anti-cancer treatment. The procedures to be performed at this examination are those defined for Visit 14 (see Section 6.3.9). Note that if a CT-scan has been performed at the last administration of study treatment this will not be repeated.

In addition, all patients who have withdrawn from study treatment will be followed every 6 months after the last contact for up to 5 years from the date of first study treatment administration to document disease recurrence, survival and safety parameters (until another cancer treatment is initiated). The procedures at these examinations are the same as for patients who have completed study treatment (See Section 6.3.10.1).

For female patients withdrawing because of pregnancy or decision to become pregnant, in addition to the follow-up of the melanoma, there will be a follow-up of the pregnancy as described in Section 8.12.

There are two exceptions to this follow-up:

- a. Patients who have withdrawn from the study because of withdrawal of consent will not be contacted again.
- b. Patients who were withdrawn from study treatment because of disease relapse or who relapsed during the post-treatment study period will not be asked to return for study follow-up visits. These patients will be contacted yearly, e.g., by telephone, to follow them for survival.

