3.2. Duration of study participation

The total duration of the study treatment phase (from first study visit to concluding visit) is 30 months per patient.

The duration of active follow-up for survival, recurrence and serious adverse events (SAEs) related to the study participation will be 5 years from the first administration of study treatment (refer to Section 8.6).

[figure not shown]

Figure 2. Overview of Design and Duration of Study.

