6.3.11. Annual contact

The survival of patients withdrawn from the study treatment because of relapse during the treatment phase or who relapsed during the follow-up period will be monitored by contacting them once a year up to 5 years after the first administration. These contacts will be made by the investigator (or a delegate) and may be done for example by telephone.

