9.2.1. Patient withdrawal from investigational product

A patient will be considered as being withdrawn from the investigational product when he/she does not receive any further planned dose after the date of withdrawal.

The investigator will document in the CRF whether the decision to discontinue further treatment was made by the patient or the investigator and which of the following possible reasons was responsible for withdrawal:

- (Serious) adverse event (including intercurrent illness, unacceptable toxicity)
- Disease recurrence
- Protocol violation
- Other (specify)

In case of withdrawal from the investigational product, the concluding visit will be performed as described in Section 6.3.9 and the patient will enter the follow-up phase with follow-up visits up to five years after first study dose. If the withdrawal from the study treatment is due to disease recurrence, the patient should be asked to come for the concluding visit but will not be asked to return for the six-monthly follow-up visits. The investigator will contact these patient once a year, e.g., by telephone, until 5 years after the first administration of the study treatment.

If the patient refuses or cannot undergo these study procedures, (s)he will be considered as withdrawn from the study (Section 9.2.2).

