9.2.2. Patient withdrawal from the study

A patient will be considered as being withdrawn from the study when (s)he does not undergo any further planned study activity after the date of withdrawal.

CONFIDENTIAL

A patient may voluntarily discontinue participation in this study at any time. The investigator may also, at his/her discretion, discontinue the patient from participating in this study at any time. In addition, if the sponsor decides to discontinue the study, no further study procedures (including administration of the study treatment) will occur.

Information relative to the withdrawal will be documented on the Study Conclusion page of the CRF. The investigator will document whether the decision to withdraw from the study was made by the patient or the investigator and which of the following possible reasons was responsible for withdrawal:

- Death (any cause),
- (Serious) adverse event (including intercurrent illness, unacceptable toxicity),
- Disease recurrence,
- Consent withdrawal, not due to an adverse event,
- Lost to follow-up,
- Other (specify).

The investigator will contact these patients once a year, e.g., by telephone, until 5 years after the first administration of the study treatment.

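### Section 6.3.10.2 leaves unclear whether recurrence and survival are still followed once a patient who stopped without relapse starts another cancer treatment

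*Combined protocol and SAP*

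**What the plan says.** **The clause.** Section 6.3.10.2 has patients who left study treatment seen every six months, up to 5 years from the first dose, "to document disease recurrence, survival and safety parameters (until another cancer treatment is initiated").

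**Follow-up elsewhere, with no stop at new therapy.** Section 3.2 says that active follow-up for survival, recurrence and related SAEs "will be 5 years from the first administration of study treatment". Section 6.2.3 applies the same schedule to patients who withdraw for reasons other than recurrence. Note (d) of Section 6.3.10 names only two end points, 5 years or recurrence. Section 9.2.1 says that after withdrawal from the product "the patient will enter the follow-up phase with follow-up visits up to five years after first study dose".

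**Relapsed patients.** Exception (b) of Section 6.3.10.2 says "These patients will be contacted yearly, e.g., by telephone, to follow them for survival". Section 6.3.11 agrees: survival after relapse "will be monitored by contacting them once a year up to 5 years after the first administration".

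**Safety period.** Sections 3.2 and 6.2.3 follow related SAEs to 5 years. Section 8.6 records pIMDs from Visit 1 to the end of the follow-up period.

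**Analysis.** Sections 10.2.1 and 10.4.2 censor patients without an event at their last assessment. Neither has a rule for new anti-cancer therapy before relapse. The RFS sensitivity analyses in Section 10.7.3.1.1 deal with missed visits and covariate adjustment.

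**Consent withdrawal.** Exception (a) of Section 6.3.10.2 says "Patients who have withdrawn from the study because of withdrawal of consent will not be contacted again". Section 9.2.2 lists reasons for leaving the study, consent withdrawal among them, and then says "The investigator will contact these patients once a year, e.g., by telephone, until 5 years after the first administration".

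**The concern.** Read broadly, the parenthesis ends recurrence follow-up when another cancer treatment begins. The patients exposed are those who stop without a recorded relapse and then start such a treatment. The protocol foresees them. Section 5.2.1.2 lists other anti-cancer treatment (b) and treatment-related grade 3 or 4 toxicity (d) as stopping reasons separate from relapse (a). Section 6.3.12 does not count a new primary cancer as relapse, yet its treatment could trigger the clause.

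Patients given another treatment are unlikely to share the prognosis of those who are not, so censoring them at the last assessment may be informative. The trial is open label and only one arm receives Poly IC:LC, so the proportion could differ by arm. The plan says it compares patients by assigned arm (Sections 10.4.2 and 10.6.1), and that comparison needs events after a switch to be recorded.

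**Working it through.** **1. The two readings against the other sections**

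| Item | Parenthesis limits all three items | Parenthesis limits safety only |
|---|---|---|
| Recurrence, no relapse yet | Stops at new therapy; conflicts with 3.2, 6.2.3, 6.3.10(d), 9.2.1 | Continues to 5 years |
| Survival, no relapse yet | Scheduled visits stop; 6.3.11 covers relapsed patients only; 9.2.2 may supply a yearly contact | Continues to 5 years |
| Related SAEs and pIMDs | Stop; conflict with 3.2, 6.2.3, 8.6 | Stop; same conflict |
| Patients with recorded relapse | RFS event already counted; yearly survival contact | Same |

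Neither reading is consistent with the rest of the protocol.

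**2. The plan's RFS power**

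Inputs from Section 10.3: 20 per arm, median RFS 12 against 24 months (hazard ratio 0.5 if exponential), one-sided 0.05, 2.5 patients per month (40/2.5 = 16 months' accrual, A), then F = 36 months. Stated power: about 61%.

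Probability of an event under uniform accrual, with λ = ln 2/median:
p = 1 − [exp(−λF) − exp(−λ(F+A))]/(λA)

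- Median 12: p = 1 − (0.125 − 0.0496)/0.924 = 0.918, so 18.4 events.
- Median 24: p = 1 − (0.3536 − 0.2227)/0.462 = 0.717, so 14.3 events.
- Total: 32.7 events.

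Freedman: Φ(√32.7 × (1 − 0.5)/(1 + 0.5) − 1.645) = Φ(1.906 − 1.645) = 60.3%. A simulated log-rank test gives 62.5%. The stated figure is reproduced.

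**3. Cost of lost events**

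The same formula with 2, 4 and 6 fewer events gives 58.0%, 55.6% and 53.1%, about 1.2 points per event.

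**4. Illustrations of bias on the broad reading**

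The documents give no rate of switching before relapse, so every rate below is an assumption.

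*Harsh case.* Design as in step 2, 20,000 simulated trials. An assumed share of patients leave follow-up one month before their relapse would be recorded. The hazard ratio is the ratio of events per unit of follow-up time.

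| Share leaving (control / combination) | True HR 0.5: power | True HR 0.5: HR estimate |
|---|---|---|
| 0% / 0% | 62.5% | 0.50 |
| 5% / 5% | 60.7% | 0.50 |
| 10% / 10% | 58.5% | 0.50 |
| 20% / 20% | 55.2% | 0.49 |
| 0% / 10% | 71.3% | 0.45 |
| 10% / 0% | 50.3% | 0.55 |

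The higher rejection rate in the 0% / 10% row comes from bias and is no gain. With no true difference, 10% leaving in the combination arm only raises the one-sided error from 5.5% to 9.1%; 20% raises it to 15.1%.

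*Milder case.* No true effect, 200,000 per arm. Assumed: 25% of patients have 1.5 or 3 times the hazard; all switchers come from that group; 5% switch in one arm and 15% or 25% in the other; switch time is uniform over 0–12 months; base median is 12 or 24 months; follow-up ends at 60 months. Censoring at the switch moves the Cox hazard ratio from 1.00 to 0.91–0.98 over the eight combinations and loses 4–12% of events. The 0.91 arises only with 25% switching, 3 times the hazard and a 24-month median; the other seven give 0.94–0.98.

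**5. Scale**

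SE of the log hazard ratio ≈ √(1/18.4 + 1/14.3) = 0.35. A shift to 0.91 is |ln 0.91|/0.35 = 0.094/0.35 ≈ 0.27 SE.

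**The case against.** A reader might infer that follow-up simply ends at another cancer treatment, and that RFS and OS are therefore informatively censored throughout the trial. The documents do not support this, for four reasons.

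- The parenthesis directly follows the safety item and may qualify it alone. Note (d) of Section 6.3.10, in the parent section, favours that reading for recurrence and survival, and the RFS and OS loss is then nil.
- Relapsed patients, probably the main group to start new therapy, already have their RFS event and keep yearly survival contact.
- Section 6.3.12 counts several starts of another therapy, after equivocal findings or unexplained symptoms, as relapse. Those are events.
- A reader might also infer that no contact rule is left for non-relapsed switchers, because Section 6.3.11 speaks only of "The survival of patients withdrawn from the study treatment because of relapse during the treatment phase" or in follow-up. But Section 9.2.2 includes adverse events and other reasons in its list and requires yearly contact to 5 years, so survival contact does not plainly lapse.

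On size, 25% against 5% switching means 5 patients against 1 with 20 per arm, all within a year and without recorded relapse. Nothing in the documents supports that. Section 10.3 expects little toxicity in either arm, and stopping treatment is not the same as starting another one.

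All of this stands, and it narrows the point to one subgroup. It does not remove the conflict: the narrow reading still contradicts the 5-year safety follow-up, and nothing in the analysis plan protects RFS if sites apply the broad reading.

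**Conclusion.** The point holds for patients who stop study treatment without a recorded relapse and then start another cancer treatment. Section 6.3.10.2 can be read as ending their recurrence follow-up, against four other sections, and Sections 10.2.1 and 10.4.2 would then censor them at the last assessment. Informative censoring of RFS is possible in this subgroup. For OS it is less clear, because of Section 9.2.2.

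The size cannot be determined from the documents and may be small. Similar switching in both arms costs mainly power and leaves the hazard ratio nearly unchanged. Material bias needs a meaningful and unequal number of such patients. Both simulations rest on assumed rates. RFS and OS are secondary endpoints, and the antibody endpoint is not touched. On either reading the late safety follow-up is inconsistent; Section 10.1.1 closes the primary safety window 30 days after the last dose, so this mainly concerns longer-term related SAEs and pIMDs.

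The conflict between Sections 6.3.10.2 and 9.2.2 over contact after consent withdrawal is separate and does not depend on the parenthesis. The list in Section 9.2.2 also includes death, so its contact sentence cannot literally cover every reason given, but as written sites cannot follow both sections.

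**What to change.** 1. State in Section 6.3.10.2 that recurrence and survival are followed to 5 years from the first dose whatever later cancer treatment is given.
2. Say what the parenthesis governs, and reconcile the safety period with Sections 3.2, 6.2.3 and 8.6.
3. Extend the annual contact in Section 6.3.11 to patients who start another cancer treatment without relapse.
4. Add to Section 10.7.3.1.1 an RFS sensitivity analysis for new anti-cancer therapy before relapse, for example counting its start as an event. Report the number of such patients by arm.
5. Separately, reconcile Section 9.2.2 with exception (a) of Section 6.3.10.2 on contact after consent withdrawal.

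Cost: protocol wording, a few extra telephone contacts and one extra analysis.

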8.6. Time period, frequency, and method of detecting adverse and serious adverse events

All AEs occurring within 30 days following administration of each dose of the study treatment must be recorded on the Adverse Event form in the patient's CRF, irrespective of intensity or whether or not they are considered to be related to the treatment administration.

The standard time period for collecting and recording SAEs (except autoimmune SAEs see below) will begin at randomization or the first receipt of study treatment and will end at the concluding visit (Visit 14, Month 30) or until 30 days after the administration of the last dose of study treatment in the event of early discontinuation of study treatment administration. See Section 8.9 for instructions on reporting and recording SAEs.

Onsets of potential immune mediated diseases (pIMD) or autoimmune disease occurring throughout the study (from Visit 1 until the end of the follow-up period) must be recorded as AE or SAE, as appropriate, in the patient CRF (see Section 8.3). Appropriate documentation of the diagnosis of autoimmune diseases must be provided in each instance.

An overview of the protocol-required reporting periods for adverse events and serious adverse events is given in Table 9.

Study activity	Screening phase	Treatment phase				Concluding visit	Follow-up
	From ICF signature to Visit 1	Visit 1	30 days post Visit 1	Visit X (X=2 to 13)	30 days post Visit X	Visit 14	Till 5 years after first administration or study withdrawal
Reporting of AEs ^a							
Reporting of SAEs ^a							
Reporting of autoimmune diseases							
Reporting of SAEs related to study participation and concurrent GSK medications ^b							

CONFIDENTIAL

- i. Except autoimmune AEs and SAEs which are reported till end of follow-up.
- j. Surgical resection of the tumor and adjuvant chemotherapy administration are not considered as study procedures; SAEs related to these treatments should not be recorded.

Table 10. Reporting periods for adverse events and serious adverse events

The investigator will inquire about the occurrence of AEs/SAEs and pIMD at every visit/contact during the study and throughout the follow-up period.

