8.11. Post-study adverse events and serious adverse events

A post-study AE/SAE is defined as any event that occurs outside of the AE/SAE detection period defined in Section 8.6. Investigators are not obligated to actively seek AEs or SAEs in former study participants.

However, if the investigator learns of any SAE, including a death, at any time after a patient has been discharged from the study, and (s)he considers the event reasonably related to the investigational product, the investigator will promptly notify the Study Contact for Reporting SAEs.

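### The plan sets a 5-year window for immune-mediated disease and study-related SAEs, but after the relapse visit no procedure list assigns their collection to the yearly contact

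*Combined protocol and SAP*

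**What the plan says.** Four groups of statements bear on this.

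- **The window.** Section 3.2: "The duration of active follow-up for survival, recurrence and serious adverse events (SAEs) related to the study participation will be 5 years" from first dose; 6.2.3 agrees. Section 8.6 says that onsets of pIMD or autoimmune disease "occurring throughout the study (from Visit 1 until the end of the follow-up period) must be recorded as AE or SAE". The last column of Table 10 is headed "Till 5 years after first administration or study withdrawal", which does not name relapse. Section 8.6 also has the investigator ask about AEs, SAEs and pIMD at each visit or contact through follow-up.
- **The end of visits.** Section 6.3.10, item d: "Five-year follow-up is performed until five years after first administration or until recurrence of disease". Sections 6.3.10.1 and 6.3.10.2(b) stop follow-up visits once relapse is established. Table 7, which lists pIMD and related-SAE recording, applies to patients who completed treatment or left it for reasons other than recurrence.
- **The contact that remains.** Section 6.3.10.2(b): "These patients will be contacted yearly, e.g., by telephone, to follow them for survival". Sections 6.2.3 and 6.3.11 give the same purpose. Sections 6.3.10.1 and 9.2.1 describe a yearly contact without stating a purpose. Sections 6.2.3 and 6.3.10.1 label it post-study.
- **A further limit.** For patients withdrawn from treatment, 6.3.10.2 follows safety parameters only until a new cancer treatment starts.

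In the analysis, 10.6.3 counts a patient with no reported event as a patient without the event, and 10.7.5.2 summarises by arm the SAEs occurring at any time after study initiation.

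**The concern.** The documents give three different end points for long-term safety collection: 5 years (or study withdrawal), recurrence, and the start of another cancer treatment. They do not say which one governs after relapse. Most patients in this population are expected to relapse within 5 years, so the choice decides how much long-term pIMD information the trial obtains.

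If collection stops with the visits, its length depends on relapse, which the plan hopes will differ between arms. Crude counts of late pIMDs or SAEs would then be drawn from unequal observation time, and patients who were no longer asked would sit in the denominator as event-free. Table 9 and section 8.3.1 make pIMD the adverse event of specific interest, so the long-term record of it should be interpretable.

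**Working it through.** **Passages side by side.** A site working from 8.6 would ask about pIMD at the yearly contact, since 6.3.11 is itself titled as an annual contact. A site working from 6.2.3, 6.3.10.2(b), 6.3.11 and Table 7 would ask about survival. Sections 6.3.9 and 6.3.12 require the Visit 14 procedures at relapse, including AE, SAE and pIMD recording, so events up to that visit are captured. Nothing equivalent is listed for the contacts that follow.

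**Inputs** (section 10.3): median RFS 12 months for ASCI alone, and 24 months that Poly IC:LC might achieve; 20 patients per arm; accrual 2.5 per month, so 40/2.5 = 16 months; 3 years of further follow-up; one-sided 0.05. Assumptions: exponential RFS, randomization taken as first dose, no other withdrawal.

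**1. The plan's own RFS power.** With λ = ln 2/median, A = 16 and F = 36, P(event) = 1 − [e^(−λF) − e^(−λ(A+F))]/(λA).

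- ASCI alone: 0.918 × 20 = 18.37 events.
- Combination: 0.717 × 20 = 14.34 events.
- Total: 32.71 events.
- Freedman: Φ(√32.71 × 0.5/1.5 − 1.645) = Φ(0.26) = 60.3%.

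The plan states about 61%, so the exponential reading of its medians is reasonable.

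**2. Visit-based surveillance if collection stops at the RFS event.** P(event by 60 months) = 1 − 2^(−60/m). Mean observed time = (m/ln 2)(1 − 2^(−60/m)).

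| | m = 12 | m = 24 |
|---|---|---|
| RFS event by month 60 | 1 − 2^(−5) = 96.9% | 1 − 2^(−2.5) = 82.3% |
| Mean observed months | 17.31 × 0.969 = 16.8 | 34.62 × 0.823 = 28.5 |
| Share of 60 months | 28% | 48% |
| Mean observed by month 30 | 14.25 | 20.07 |
| Share of months 30–60 observed | (16.77 − 14.25)/30 = 8% | (28.50 − 20.07)/30 = 28% |

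The ratio of mean observed time is 28.5/16.8 = 1.7.

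**3. Without the hoped-for benefit.** Section 1.1 cites 90% recurrence at five years. That implies a median of 60 × ln 2/ln 10 = 18.1 months and a mean of 0.9 × 60/ln 10 = 23.5 months. If both arms followed that curve, under 40% of the window would be observed (23.5/60 = 39%), with no difference between arms.

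**4. What this means in patients.** The documents give no pIMD rate, so I assume the same true 5-year risk r in both arms, with constant independent hazards. With h = −ln(1 − r)/60, the captured proportion is h/(h + λ) × [1 − e^(−60(h + λ))].

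| r (assumed) | ASCI alone | Combination | Patients per 20 |
|---|---|---|---|
| 5% | 1.4% | 2.4% | 0.3 vs 0.5 |
| 10% | 2.9% | 4.8% | 0.6 vs 1.0 |
| 20% | 5.9% | 9.8% | 1.2 vs 2.0 |

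The apparent ratio is about 1.7 with no true difference, but the gap between arms is under one patient throughout.

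**The case against.** The best defence is that 8.6 is the governing safety section. It runs pIMD collection to the end of follow-up and asks at each visit or contact, and none of the descriptions of the yearly contact says survival only. This has force. A reader might infer that surveillance definitely ends at relapse and that the 5-year promise is broken. The documents do not support that: they conflict, and a site following 8.6 would keep asking. What remains is that no procedure list carries the 8.6 instruction into the yearly contact.

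A reader might also take 8.11 as confirmation: "Investigators are not obligated to actively seek AEs or SAEs in former study participants". It is not. That section covers only events outside the 8.6 detection period, so it cannot show when the period ends, and it still requires prompt notification of SAEs that the investigator learns of and considers reasonably related to the product.

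The limit at new cancer treatment may be deliberate, because later events are hard to attribute. That is a legitimate design choice, but it is a third end point and does not match 3.2, 8.6 or Table 10.

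The strongest inference would be that the primary safety comparison is biased between arms. It does not follow. Section 10.1.1 closes the SAE and autoimmunity endpoint 30 days after the last dose. Relapse stops dosing, and 6.3.10.2 places the withdrawal examination at least 30 days after that dose, so the window is largely covered. No between-arm test of pIMD is specified. Because dosing stops at relapse, the later-relapsing arm would also receive more doses, so a pIMD difference would not reflect observation time alone.

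Finally, the 24-month median is a hope, and RFS events include deaths, after which there is nothing left to observe. The surveillance figures therefore overstate the part of the gap that the protocol could close.

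**Conclusion.** The inconsistency stands and is worth correcting. The protocol does not settle whether pIMD and study-related SAEs are collected between the relapse visit and year 5. If sites follow section 6, roughly 28% of the 60-month window is observed in the ASCI arm and 48% in the combination arm.

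The incompleteness does not depend on a treatment benefit; the 1.7-fold difference between arms does. Both rest on exponential RFS and on no other withdrawal. In absolute terms the distortion is small at this sample size. The harm is to the interpretability of long-term pIMD and SAE summaries, particularly because 10.6.3 treats unasked patients as event-free and no person-time analysis is planned.

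**What to change.** Reconcile 6.2.3, 6.3.10(d), 6.3.10.1, 6.3.10.2, 6.3.11, 8.6, Table 7 and Table 10 in one of two ways.

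- **Preferred.** State that the existing yearly contact, besides survival, asks about new pIMD (using the questionnaire already named in 8.3.1) and SAEs related to study participation, and records the start date and type of any new anticancer treatment. Add the contact as a column in Table 7, and say in 8.6 and Table 10 that the window runs to 5 years whether or not the patient relapses. Show onsets before and after new treatment separately.
- **Alternative.** If collection is meant to stop at relapse or at new treatment, say so in 3.2, 8.6 and Table 10, and report long-term pIMD and SAEs per person-time observed in each arm.

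The preferred option costs protocol wording and a few questions on a contact already planned, with no new visit or procedure. Its small downside is that events after new therapy are harder to attribute, which the recorded start date partly handles. On the recruitment dates anticipated in Appendix A (March 2011 to February 2013), 5-year windows would close between about March 2016 and February 2018. That is after this version's date of October 2015, so the change could still have affected what is collected.
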